8.6.3.1 Follow-up Information

Additional information may be added to a previously submitted report by any of the following methods:

- Adding to the original MedWatch 3500A report and submitting it as follow-up
- Adding supplemental summary information and submitting it as follow-up with the original MedWatch 3500A form
- Summarizing new information and faxing it with a cover letter including patient identifiers (i.e. D.O.B. initial, patient number), protocol description and number, if assigned, brief adverse event description, and notation that additional or follow-up information is being submitted (The patient identifiers are important so that the new information is added to the correct initial report)

Occasionally Genentech may contact the reporter for additional information, clarification, or current status of the patient for whom an adverse event was reported. For questions regarding SAE reporting, you may contact the Genentech Drug Safety representative noted above or the MSL assigned to the study. Relevant follow-up information should be submitted to Genentech Drug Safety as soon as it becomes available and/or upon request.

MedWatch 3500A (Mandatory Reporting) form is available at http://www.fda.gov/medwatch/getforms.html

8.7 Study Close-Out

Any study report submitted to the FDA by the Sponsor-Investigator should be copied to Genentech. This includes all IND annual reports and the Clinical Study Report (final study report). Additionally, any literature articles that are a result of the study will be sent to Genentech. Copies of such reports will be mailed to the assigned Clinical Operations contact for the study:

[contact]

8.7.1: Additional Reporting Requirements for IND Holder

For Investigator-Initiated IND Studies, events meeting the following criteria will be submitted to the Food and Drug Administration (FDA) as expedited IND Safety Reports according to the following guidance and timelines:

8.7.1.1 7 Calendar Day Telephone or Fax Report

The Investigator will notify the FDA of any fatal or life-threatening adverse event that is unexpected and assessed by the Investigator to be possibly related to the use of Pulmozyme. An unexpected adverse event is one that is not already described in the Pulmozyme investigator Brochure. Such reports are to be telephoned or faxed to the FDA, Genentech, and IRB within 7 calendar days of first learning of the event. A copy of the report will be submitted to the NEI Program Official within 24 hours of FDA notification.

8.7.1.2 15 Calendar Day Written Report

The Investigator will notify the FDA, and IRB in a written IND Safety Report, of any serious, unexpected AE that is considered reasonably or possibly related to the use of Pulmozyme. An unexpected adverse event is one that is not already described in the Pulmozyme investigator brochure. A copy of the report will be submitted to the NEI Program Official.

Written IND Safety reports will include an Analysis of Similar Events in accordance with regulation 21 CFR § 312.32. All safety reports previously filed by the investigator with the IND concerning similar events will be analyzed and the significance of the new report in light of the previous, similar reports commented on.

Written IND safety reports with Analysis of Similar Events will be submitted to the FDA and Genentech within 15 calendar days of first learning of the event. The FDA prefers these reports on a MedWatch 3500 form, but alternative formats are acceptable (e.g., summary letter).

8.8 Fax number for IND Safety Reports:

All written IND Safety Reports submitted to the FDA by the Investigator will also be faxed to Genentech Drug Safety, and to the IRB at UIC.

FDA: [name]

8.9 In Case of an Emergency

In medical emergencies, the Investigator should use medical judgment and remove the subject from immediate hazard. The IRB should be notified as to the type of emergency and the course of action taken. The blind will be broken for ADR reports that are Serious and Unexpected The CRF and the source document for the subject must describe the departure from the protocol and state the reason.

8.10 Data Safety Management Plan

The study protocol will be reviewed and approved by the UIC IRB. Adverse events and compliance will be monitored. Research staff will be trained on the protocol requirements and data collection methods before completing study related procedures.

8.11 Study Oversight

The Study PI has primary oversight responsibility for this study. [name] is a board certified Ophthalmologist with an active practice in the area of Dry Eye Disease. He routinely takes care of patients with severe ocular surface disease, especially those with ocular GVHD. He's also the director of Dry Eye service at UIC. Therefore, he's well qualified to recognize the symptoms and clinical signs of an adverse event. [name] has been the PI of past and active IRB approved clinical studies and has monitored data related to those studies. Therefore, he has experience in data and safety monitoring.

The Principal Investigator and his research team are responsible for identifying adverse events. Safety monitoring will include careful assessment and appropriate reporting of adverse events. Subjects will be reminded to inform the study staff of any adverse effects that they have experienced or are experiencing after the first administration of study drug. Subjects will be provided with diaries to record at home the time of each dose and any adverse symptoms. All reports of adverse events during the study will be recorded on an Adverse Event Case Report Form (CRF). In addition, subjects will be asked to make a note of any missed doses together with the reason for the omission. A member of the research staff will review diary entries with the subject at each study visit. Subjects will be asked to bring back the left-over drug at each study visit. The amount of drug remaining in the used vial will also give an estimate of the compliance.

Accumulated safety and data information will be reviewed after 10 subjects complete the study. The research team will then evaluate whether it is safe to proceed with the study, and if the protocol or informed consent documents require revision based on that review.

8.12 Reporting Changes in Study Status

During the funding of this study, any action by the FDA, an IRB, the industry collaborator (Genentech), or one of the study investigators that results in a temporary or permanent suspension of the study will be reported to the NEI Program Official within 3 business days of notification.

9 Data Quality and Safety Review Plan and Monitoring

9.1. Data Quality and Management

9.1.1. Plan for Data Quality and Management: The PI or study staff will review all data collection forms on an ongoing basis for data completeness and accuracy as well as protocol compliance.

9.1.2. Frequency of Data Review for this Study: The frequency of data review for this study differs according to the type of data and can be summarized in the following Sample Table

Data type	Frequency of review	Reviewer
Subject accrual (including compliance with protocol enrollment criteria)	Semiannually	PI, Independent Monitor
Status of all enrolled subjects, as of date of reporting	Semiannually	PI, Independent Monitor
Adherence data regarding study visits and intervention	Semiannually	PI, Independent Monitor
AEs and rates (including out- of-range lab values)	Semiannually	PI, Independent Monitor
SAEs	Per occurrence	PI, Independent Monitor FDA, NEI Program Official

9.2. Subject Accrual and Compliance

- **9.2.1.** Measurement and Reporting of Subject Accrual, Compliance With Inclusion/Exclusion Criteria: Review of the rate of subject accrual and compliance with inclusion/exclusion criteria will occur semiannually to ensure that a sufficient number of participants are being enrolled and that they meet eligibility criteria and the targeted ethnic diversity goals outlined in the grant proposal.
- **9.2.2.** Measurement and Reporting of Participant Adherence to Treatment Protocol: Data on adherence to the treatment protocol will be collected by research staff and reviewed semiannually by the PI and the Independent Medical Monitor. Adherence of participants will be evaluated by performing eyedropper counts and by reviewing patient diaries at each visit. If adherence falls below 75%, which might inhibit the ability of the study to test its primary hypotheses, the Independent Medical Monitor will suggest a conference call for study investigators to discuss methods for improving adherence.
- **9.3.** Stopping Rules: This study will be stopped prior to its completion if: (1) the intervention is associated with adverse effects that call into question the safety of the intervention; (2) difficulty in study recruitment or retention will significantly impact the ability to evaluate the study endpoints; (3) any new information becomes available during the trial that necessitates stopping the trial; or (4) other situations occur that might warrant stopping the trial. The PI will include an assessment of futility in the annual progress report to NEI and will consult with the study monitors to assess the impact of significant data loss due to problems in recruitment, retention, or data collection.

9.4 Data and Safety Monitoring Board (DSMB): The PI has designated a Data and Safety Monitoring Board to perform an independent review of ongoing study progress and safety. The Monitoring Board for this study is comprised of three voting members: [name] who is also the independent monitor, [name]. and [name]. [name], [name], and [name] are not associated with this research project and thus work independently of the PI, [name]. They are not part of the key personnel involved in this grant. They are qualified to review the patient safety data generated by this study because of their unique expertise in the area of clinical trials, ophthalmological diseases and epidemiology/biostatistics. [name], who is the Director of the UIC Center for Ophthalmology Clinical Trials and Translational Studies (CO-CTTS), has experience in epidemiologic studies, therefore will be the chairperson of the DSMB. [name], [name], and [name] view their role as representing the interests of the patients enrolled in the trial and not those of UIC. Drs. [name], [name], and [name] report no conflict of interest that includes financial interest or professional interest (in the sense of the trial outcome benefiting the individual professionally) or proprietary interest. The PI will be a non-voting ex-officio member of the DSMB. DSMB will meet at

least annually. Interim meetings may be held at the request of DSMB members, the study leadership, or the NEI.

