The most likely discomforts a subject may experience by using rhDNase I administered as eye drops are eye burning or irritation, red watery eyes, or feeling like there is something in the eye. To see how subjects react to the study medication, their first dose will be given by the investigator in the clinic itself. Afterwards subjects will be asked to rate tolerability of the drug on the Visual Analogue Scale. Also, at each visit, subjects will be asked to complete the Visual Analogue Scale.

An allergic reaction to the drug cannot be predicted beforehand. In event of an allergic reaction, the drug will be stopped immediately, and symptoms will be managed appropriately depending on the severity of the reaction.

No single agent has yet been approved by the FDA for GVHD prevention or therapy.³⁴ Contact lenses, commonly used to treat oGVHD, will be withheld during the 14 day wash-out period and over the entire course of the study. Stopping contact lens wear may increase the subject's risk of worsening oGVHD. All study subjects will be encouraged to contact the research team immediately if they experience worsening of oGVHD.

No psychological, social, legal, or financial risk is expected from participating in the research.

There is always a risk of a loss of confidentiality.

2 Study Objectives

The objective of this study is to establish whether patients with ocular graft-vs.-host disease (oGVHD) are able to tolerate receiving rhDNase I 0.1% eye drops four times a day for eight weeks (primary tolerability objective) and to investigate the preliminary efficacy of rhDNase I 0.1% topical eye drop solution in treating oGVHD (primary efficacy objective).

3 Study Design

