9.4.1 Responsibilities of the DSMB

- Review and approve the research protocol(s) and plans for data and safety monitoring.
- Review interim analyses of outcome data and cumulative toxicity data for safety and efficacy to determine whether the trial should continue as originally designed, should be changed, or should be terminated.
- Review and approve the primary trial manuscript(s) with regard to determining that the results are fairly presented and the conclusions appropriate.
- Review proposed modifications to the study prior to their implementation
- Following each DSMB meeting, provide the study leadership and the NEI with written recommendations related to continuing, changing, or terminating the trial.
- **9.5 Safety Review Plan:** Study progress and safety will be reviewed semiannually (and more frequently if needed). Progress reports, including patient recruitment, retention/attrition, and AEs will be provided to the Independent Medical Monitor following each of the semiannual reviews. An Annual Report will be compiled and will include a list and summary of AEs. In addition, the Annual Report will address (1) whether AE rates are consistent with pre-study assumptions; (2) reason for dropouts from the study; (3) whether all participants met entry criteria; (4) whether continuation of the study is justified on the basis that additional data are needed to accomplish the stated aims of the study; and (5) conditions whereby the study might be terminated prematurely. The Annual Report will be sent to the Independent Medical Monitor and will be forwarded to the DMSB, IRB, NEI Official, FDA, and industry collaborator. The PI will also send copies of recommendations and comments from the Independent Medical Monitor or Chair of the DSMB to the NEI Program Officer within 2 months of each monitoring review.

10 Confidentiality

Information about study subjects will be kept confidential and managed according to the requirements of the Health Insurance Portability and Accountability Act of 1996 (HIPAA). Those regulations require a signed subject authorization informing the subject of the following:

- What protected health information (PHI) will be collected from subjects in this study
- Who will have access to that information and why
- Who will use or disclose that information
- The rights of a research subject to revoke their authorization for use of their PHI.

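### The toxicity stopping statement in 9.3 is qualitative and unreconciled with 8.11 and 9.4.1, and a non-serious eye event that ends treatment reaches the Independent Monitor only at semiannual review

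*Combined protocol and SAP*

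**What the plan says.** - **9.3 Stopping Rules.** Limb (1) applies when "the intervention is associated with adverse effects that call into question the safety of the intervention". The other limbs cover recruitment or retention difficulty, new information, and other situations. No limb says who decides.
- **9.1.2 table.** The row "AEs and rates (including out- of-range lab values") is semiannual, for the PI and the Independent Monitor. The serious adverse event row is "Per occurrence", and it is the only row with that frequency.
- **8.11 Study Oversight.** "Accumulated safety and data information will be reviewed after 10 subjects complete the study". Then: "The research team will then evaluate whether it is safe to proceed with the study". No criterion is given.
- **9.4 and 9.4.1.** The DSMB meets at least once a year, with extra meetings if its members, the study leadership or the NEI ask. It reviews cumulative toxicity and recommends continuing, changing or terminating. The independent monitor is one of its three voting members.
- **9.5.** Safety review is semiannual, or more frequent where necessary. The Annual Report covers reasons for dropout and "whether AE rates are consistent with pre-study assumptions".
- **1.5, 5.7, 3.4, 8.1 and 8.4.** The most likely discomforts are "eye burning or irritation, red watery eyes, or feeling like there is something in the eye". Discontinuing study drug is one of three responses the PI may choose for worsening or an adverse event, and it entails withdrawal. The primary safety endpoint is the proportion completing eight weeks of four-times-daily drops. Subjects withdrawn for adverse events may be replaced. Section 8.4 already records whether an event caused withdrawal.

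**The concern.** The trial puts an inhaled product into the eye, and the direct topical experience cited in 1.4 is one published case. The effects 1.5 regards as most likely would often meet none of the seriousness criteria in 8.1, yet any of them could be a reason to discontinue under 5.7. Such an event counts against the primary safety endpoint, but 9.1.2 places it with all other adverse events for semiannual review.

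Two things are at stake. First, several subjects could stop drops for eye intolerance while enrolment continues, with no scheduled step bringing this promptly to the one person who is both independent of the study team and on the DSMB. Second, if a signal appears, 8.11, 9.3 and 9.4.1 do not agree on whose judgement governs. Section 9.2.2 handles adherence more explicitly: a fall below 75% leads a named role to take a named step. A toxicity-related discontinuation has no equivalent step.

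**Working it through.** The documents attach no figure to the stopping statement, so there is none to reproduce and its error rates cannot be calculated. The check is a comparison of sections followed by simple timing arithmetic.

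**1. Path of a non-serious eye event that ends treatment**

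| Step | Section | When | Who | Criterion |
|---|---|---|---|---|
| Drug stopped, subject withdrawn | 5.7 | At the event | PI, masked | Clinical judgement |
| Review of 10 completers | 8.11 | Once | Research team, masked | None |
| Adverse event review | 9.1.2, 9.5 | Semiannual, or sooner if judged necessary | PI, Independent Monitor | None |
| Cumulative toxicity | 9.4, 9.4.1 | At least yearly, or on request | DSMB | None |
| Study stop | 9.3(1) | Not stated | Not stated | Qualitative |

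The event is captured and does reach review. Before the next scheduled review, however, it reaches the monitor only if somebody chooses to raise it.

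**2. Review interval against treatment length**

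Inputs: treatment of 8 weeks (Study Summary, 5.2); semiannual review, taken as 26 weeks; even accrual (assumption).

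- Subjects starting in the first 26 − 8 = 18 weeks of an interval finish treatment before its end: 18/26 = 69%.
- The longest wait from event to scheduled review is 26 weeks. The average is 26/2 = 13 weeks if events fall evenly.
- Accrual is not stated. An assumed 1 to 6 starts per month gives 6 to 36 per half-year, about half on active drug (3 to 18). Those finishing treatment before the review number 0.69 × 6 ≈ 4 to 0.69 × 36 ≈ 25, both arms together.

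**3. Timing of the 8.11 review**

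The final visit is at week 10, or 10/4.345 = 2.3 months. With *a* starts per month and *w* early withdrawals that do not count as completers, the tenth completion falls at about (10 + *w*)/*a* + 2.3 months. Each withdrawal delays it by 1/*a* months.

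| *a* per month | *w* = 0 | *w* = 3 |
|---|---|---|
| 1 | 12.3 months | 15.3 months |
| 2 | 7.3 | 8.8 |
| 3 | 5.6 | 6.6 |
| 6 | 4.0 | 4.5 |

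Early discontinuations therefore push the review back. At 2 starts per month or fewer, it also falls after the first semiannual review if that clock runs from first enrolment (assumption).

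This rests on reading completion as excluding withdrawn subjects. Section 4.4.2 asks withdrawn subjects to undergo the week 10 procedures and allows some to stay for safety follow-up, so whether they count is unclear.

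**The case against.** The strongest reply is that this is a small single-site trial with a DSMB whose remit includes termination and is not confined to serious events. A judgement-based stopping statement is a legitimate choice in that setting, and numeric limits are a preference. The informal routes are also short. The PI decides each discontinuation and, as study leadership, can ask for a DSMB meeting. The monitor sits on the DSMB and can ask too. Section 9.5 allows more frequent review. Seriousness criterion 6 in 8.1 lets the investigator class a significant eye event as serious. Withdrawals could also engage the retention limb of 9.3, and its last limb is open-ended.

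Most of this stands, and it rules out some stronger readings:

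- *That non-serious toxicity sets off nothing.* It is recorded, can lead to action for that subject, and enters the reviews in 8.11, 9.4.1 and 9.5.
- *That nobody can stop the trial.* The DSMB and the research team both have roles. What is missing is their link to 9.3 and to each other.
- *That the protocol expects drops to be stopped.* Section 1.5 lists likely discomforts, 1.4 expects no severe events, and 5.7 only permits discontinuation.
- *That the 9.5 check on adverse event rates has no comparator.* The protocol states no expected rate for the eye drops, but 8.1 defines expected events by the Package Insert or Investigator's Brochure, which are not available here.

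The reply leaves the routing gap open. Every early route depends on discretion, the monitor cannot ask for a meeting about events not yet reported, and the 8.11 review is held by a masked team on a clock that withdrawals do not advance.

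**Conclusion.** The point holds as a gap in routing and reconciliation. Section 9.3(1) is qualitative and is not connected to the roles in 8.11 and 9.4.1. A non-serious eye event that ends treatment has no per-occurrence path to the Independent Monitor, although it is a failure on the primary safety endpoint.

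The scheduled wait is up to 26 weeks against an 8-week course. About 69% of subjects starting in an interval finish treatment before its review. The percentage rests on even accrual and reviews exactly 26 weeks apart. The headcount of 4 to 25 also rests on the assumed 1 to 6 starts per month. The discretionary routes could shorten the wait, so these figures describe the schedule alone.

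This is a worthwhile, inexpensive improvement in safety oversight. It does not show that the trial lacks oversight.

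**What to change.** 1. In the 9.1.2 table, move adverse events that cause discontinuation of study drug, identified by the 8.4 status for events causing withdrawal, from semiannual to per-occurrence review by the Independent Monitor. The monitor can already ask for an interim DSMB meeting under 9.4.
2. Reconcile 8.11, 9.1.2, 9.3, 9.4.1 and 9.5 on who decides to continue or stop, and state whether withdrawn subjects count toward the 10 in 8.11, consistently with 4.4.2, 5.7 and the replacement provision in 8.1.

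No stopping count or boundary is proposed. Any threshold is for the DSMB and sponsor to settle. So is any release of data by arm, which would have to fit the masking in 5.3 and the code-breaking provision in 8.9. Individual reports to the monitor can stay masked.

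**Cost.** Protocol wording, some extra reports and possibly an extra ad hoc DSMB meeting. If 5% to 20% of all 72 subjects stopped for an adverse event (assumption), that is 72 × 0.05 ≈ 4 to 72 × 0.20 ≈ 14 reports over the whole trial, to a monitor already in place.

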9.4.1 Responsibilities of the DSMB

- Review and approve the research protocol(s) and plans for data and safety monitoring.
- Review interim analyses of outcome data and cumulative toxicity data for safety and efficacy to determine whether the trial should continue as originally designed, should be changed, or should be terminated.
- Review and approve the primary trial manuscript(s) with regard to determining that the results are fairly presented and the conclusions appropriate.
- Review proposed modifications to the study prior to their implementation
- Following each DSMB meeting, provide the study leadership and the NEI with written recommendations related to continuing, changing, or terminating the trial.
- **9.5 Safety Review Plan:** Study progress and safety will be reviewed semiannually (and more frequently if needed). Progress reports, including patient recruitment, retention/attrition, and AEs will be provided to the Independent Medical Monitor following each of the semiannual reviews. An Annual Report will be compiled and will include a list and summary of AEs. In addition, the Annual Report will address (1) whether AE rates are consistent with pre-study assumptions; (2) reason for dropouts from the study; (3) whether all participants met entry criteria; (4) whether continuation of the study is justified on the basis that additional data are needed to accomplish the stated aims of the study; and (5) conditions whereby the study might be terminated prematurely. The Annual Report will be sent to the Independent Medical Monitor and will be forwarded to the DMSB, IRB, NEI Official, FDA, and industry collaborator. The PI will also send copies of recommendations and comments from the Independent Medical Monitor or Chair of the DSMB to the NEI Program Officer within 2 months of each monitoring review.

10 Confidentiality

Information about study subjects will be kept confidential and managed according to the requirements of the Health Insurance Portability and Accountability Act of 1996 (HIPAA). Those regulations require a signed subject authorization informing the subject of the following:

- What protected health information (PHI) will be collected from subjects in this study
- Who will have access to that information and why
- Who will use or disclose that information
- The rights of a research subject to revoke their authorization for use of their PHI.

In the event that a subject revokes authorization to collect or use PHI, the investigator, by regulation, retains the ability to use all information collected prior to the revocation of subject authorization. For subjects that have revoked authorization to collect or use PHI, attempts should be made to obtain permission to collect at least vital status (i.e. that the subject is alive) at the end of their scheduled study period.

11 Source Documents

Source data is all information, original records of clinical findings, observations, or other activities in a clinical trial necessary for the reconstruction and evaluation of the trial. Source data are contained in source documents. Examples of these original documents, and data records include: hospital records, clinical and office charts, laboratory notes, memoranda, subjects' diaries or evaluation checklists, pharmacy dispensing records, recorded data from automated instruments, copies or transcriptions certified after verification as being accurate and complete, microfiches, photographic negatives, microfilm or magnetic media, x-rays, subject files, and records kept at the pharmacy, at the laboratories, and at medico-technical departments involved in the clinical trial.

